#### b. Study duration and number of study visits required of research participants.

1. **Duration of therapy:** Once optimal dose is found (25 mg/kg/day or maximal tolerated dose; expected to be reached within 5 weeks), participants may continue on the **Core Phase** for a minimum of 8 weeks after reaching steady state; during this time the dose of their other anticonvulsants will not be changed unless signs of toxicity or significant changes in blood levels are observed. This will be followed by 28 weeks of an **Optimization Phase** during which the subject will be followed every 6-12 weeks (see Study Visits for details) and doses of other anticonvulsants may be changed to optimize seizure control. After the Optimization Phase, subjects will be offered the opportunity to enter the **Extension phase** and continue on CBD with clinical follow-up every 3 months. Optimal dosing is proposed by GW Pharm Inc, based upon their preclinical studies and clinical experience to date.

## 2. Study Visits:

- Study Visit 1: Screening Visit: Informed consent process, eligibility criteria, provide seizure diary and instruct on use.
- Study Visit 2: Baseline Visit: Confirm eligibility and begin drug at dose 1 (see Visit Table and Dose Schedule). Provide study drug dosing record and instruct on use.

During the following Study Visits (see Visit Table), the participants will undergo clinical assessments, a neuroscore, have pictures taken, blood draws for laboratory tests, study drug accountability, concomitant medication survey, adverse event reporting, and study drug administration (see Visit Table for details).

An additional blood draw will also be necessary within 72 hours of a previous blood draw if the most recent result indicates a clinically significant ( $>3xULN$ ) elevation of ALT or AST. At minimum, the following tests should be repeated: ALT/AST, total bilirubin, and alkaline phosphatase. A GGT test will also be performed at that time. This bloodwork (ALT/AST, total bilirubin, and alkaline phosphatase and GGT test) will also be necessary if: 1) the dose of your study drug dose is increased after the escalation phase, 2) another drug which affects liver function is added, stopped, or has a dose change, or 3) you have one or more of the following symptoms without another explanation: fatigue, encephalopathy, nausea, vomiting, right upper quadrant pain or tenderness, abdominal pain or distension, fever, excessive bruising, excessive nose or gum bleeds, or petechia. All trial subjects with elevated LFTs will be followed closely until all abnormalities return to the baseline state as assessed by the investigator with  $AST/ALT < 3x ULN$  and will be followed until ALT/AST have normalized and symptoms resolve.

At the end of the Core Phase (Visit 10) and Optimization Phase (visit 14), participants will have the option between continuing in an extension study or weaning off of the study drug. Those who decide to continue will remain on the same dosage of medication and return for labs and clinical visits at least every three months or as deemed clinically necessary, and drug will be provided free of cost to the subject for at least one year, or until the drug is approved for clinical use for the treatment of epilepsy in patients with Sturge-Weber syndrome. Those who decide to wean off of the study will return for a final follow-up visit in 1 month (Week 52).

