### Laboratory tests and clinical procedures

- Weight, vitals and orthostatics will be monitored at baseline and at each visit. For subjects who are physically unable to complete standing orthostatics, only supine orthostatics will be collected. (Routine care)
- Neuroscores will be assigned at each visit by [name] as per her clinical routine. Neurologic exam and general physical exam will also be performed at each visit. (Routine care)
- Participants will be asked at each clinic visit about migraine frequency, severity (scale of 1-10) and duration, and any change in neurologic symptoms
- CBC, LFT, BUN, creatinine levels, electrolytes, will be measured at baseline, one month after baseline, one month and two months after maintenance dose steady state is reached, every 2-3 months during the Optimization Phase, and every three months (at each visit) during extension phase. Urine analysis will be performed at each of the extension phase visits (every three months).
- For subjects with a facial port-wine birthmark, frontal and profile photograph will be taken under standardized conditions with scoring of the port-wine birthmark for percent of face covered, thickness of birthmark, and darkness of birthmark color. Subjects without any facial port-wine birthmark will only need photographs taken at a single visit to confirm the lack of birthmark. (Research, See Study Visit Table)
- Concomitant AED plasma concentrations will be measured at baseline, one month after baseline, at steady state maintenance CBD dose, one month and two months after maintenance dose steady state is reached, every 2-3 months during the Optimization Phase, and at each extension phase visit.
- CBD plasma concentrations will be measured twice, at 6 and 10 weeks after baseline.
- hCG urine pregnancy test will be used for all female participants Tanner stage 2 and above (see Study Visit Table). We will tell subjects that they must be using effective birth control (for example, abstinence, birth control pills, contraceptive implants, condoms) and confirm that this is the case at each study visit. We will inform female subjects that they should not become pregnant or breastfeed a baby while on this study or for 30 days after taking Cannabidiol. We will also inform male subjects that they should not get their partners pregnant while on this study or for 30 days after taking Cannabidiol. Anyone who becomes pregnant while on the study will be removed immediately.

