### *e. Justification for inclusion of a placebo or non-treatment group.*

Not applicable for this first small expanded access study.

*f. Definition of treatment failure or participant removal criteria.*

Treatment failure will be defined as less than a 50% reduction in seizure frequency compared to baseline seizure frequency. Treatment failure will be initially assessed 14 weeks after starting drug (or 8 weeks after reaching steady state) and will be reassessed at every visit thereafter. A subject may continue with only a 30% reduction in seizure frequency if the drug is well tolerated compared to previously tried anticonvulsants. If the subject experiences a temporary increase in seizures at the time treatment failure is assessed, [name] may take the temporary nature of the increase into account. She may also look at the overall reduction in seizure frequency since treatment initiation in determining whether a subject should be withdrawn. If the subject has had other benefits to mood, behavior, or neurologic exam that outweighed the risk from an increase in seizures, then [name] may decide to decrease the dose of the study drug since it has been observed that some subjects do well at doses lower than 25mg/kg/day.

**Participant removal criteria:** If a participant experiences a significant decline in his or her health or wellbeing, the PI will remove the participant from the study. This could include a significant worsening of seizures, or the occurrence of intolerable side effects.

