**Treatment will continue until any of the following take place:**

1. Loss of seizure control defined as an increase of 50% in the average weekly number of seizures for a minimum of 4 weeks as compared to the average weekly number of partial-onset seizures during the 8 weeks baseline period. At this point, the subject's CBD dose can be decreased without requiring immediate withdrawal. The subject does not need to be withdrawn unless the seizure frequency does not drop below the 50% increase on the lowered dose.
2. Use of rescue medications longer than the maximum duration determined during the Baseline period.
3. Intolerable toxicity.
4. Treatment failure as defined above.
5. Pregnancy.
6. Withdrawal of consent.
7. Treatment duration completed as per protocol: completion of the Core phase (if patients do not accept to start the extension phase) or completion of the Extension phase.
8. Laboratory results indicate that the subject's liver function test (ALT or AST) has increased in any of the following ways:
  - >8xULN
  - >5xULN for more than 2 weeks
  - >3xULN **and** either (TBL >2xULN **or** INR >1.5)
  - >3xULN with the appearance of fatigue, nausea, vomiting, right upper quadrant pain or tenderness, fever, rash, and/or eosinophilia (>5%)

*g. Description of what happens to participants receiving therapy when study ends or if a participant's participation in the study ends prematurely.*

At study's end GW Pharmaceuticals will continue to provide drug to any patient doing well on Epidiolex and wanting to remain on it (extension study), at least until they have obtained an indication for pediatric epilepsy and it can be billed to the patient's insurance company. All others will be weaned off of the study drug over a month and seen back for one final follow-up visit one month later. For those discontinued specifically due to elevated liver function tests, they will continue to be followed until all abnormalities return to the baseline state as assessed by the investigator with AST or ALT <3xULN. Any patient removed early from the study, and all participants at the end of the study wishing to remain

**PROPRIETARY MATERIALS OF THE HUGO W. MOSER RESEARCH INSTITUTE AT KENNEDY KRIEGER, INC. DO NOT USE OR DISCLOSE WITHOUT PERMISSION OF THE RESEARCH INSTITUTE**

[name] patient will continue to be cared for by [name] and seen at the Hunter Nelson Sturge-Weber Center.

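### The liver stopping rule can turn on INR >1.5, but the repeat draw required within 72 hours of ALT or AST >3xULN does not require an INR

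*Combined protocol and SAP*

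**What the plan says.** **Stopping rule (Section 4f, conditions that end treatment, item 8).** Treatment ends when ALT or AST is:

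- above 8xULN;
- above 5xULN for more than 2 weeks;
- above 3xULN with either total bilirubin (TBL) above 2xULN or INR above 1.5; or
- above 3xULN with any of a list of symptoms and signs, or with eosinophilia above 5%.

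**Repeat draw (Section 4b, item 2, Study Visits).** "An additional blood draw will also be necessary within 72 hours of a previous blood draw if the most recent result indicates a clinically significant" elevation of ALT or AST, given there as above 3xULN. The content follows: "At minimum, the following tests should be repeated: ALT/AST, total bilirubin, and alkaline phosphatase. A GGT test will also be performed at that time". The same tests are then listed again for three other prompts: a dose increase after escalation, a change in another drug that affects the liver, and unexplained symptoms. INR is in neither list.

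**Scheduled laboratory tests (Section 4a, Laboratory tests and clinical procedures).** "CBC, LFT, BUN, creatinine levels, electrolytes, will be measured at baseline, one month after baseline", with later time points following. What LFT comprises is not defined. The section does not name INR or PT.

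**Other safeguards.** Section 4b adds: "All trial subjects with elevated LFTs will be followed closely". Section 4f also provides for removal on clinical grounds: "If a participant experiences a significant decline in his or her health or wellbeing, the PI will remove the participant from the study". Item 3 of its list of conditions ends treatment for "Intolerable toxicity".

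**The concern.** A numeric safety stop works only if its measurement is available when the rule has to be applied. The INR limb can be met only when ALT or AST is above 3xULN, and every such result leads to the 72-hour draw. That draw is therefore the natural place to secure the INR, yet its itemised panel leaves the test out. The bilirubin limb, an equal alternative in the same criterion, is covered.

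At stake is a subject whose transaminases are moderately raised, whose bilirubin is not above 2xULN, and whose INR is above 1.5. Staff who order exactly the listed tests would have nothing to set against the INR limit, and an unmeasured INR can be mistaken for a criterion not met.

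**Working it through.** No arithmetic applies, and the plan gives no figure to reproduce. The check sets what each item 8 criterion needs against what the 72-hour draw requires.

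| Item 8 criterion | Measurement needed | Required on the 72-hour draw? |
|---|---|---|
| >8xULN | ALT/AST | Yes |
| >5xULN for more than 2 weeks | ALT/AST over time | Yes, with continued follow-up |
| >3xULN and TBL >2xULN | ALT/AST, total bilirubin | Yes |
| >3xULN and INR >1.5 | ALT/AST, INR | ALT/AST yes; INR no |
| >3xULN with listed symptoms or signs | ALT/AST, clinical assessment | ALT/AST yes |
| >3xULN with eosinophilia >5% | ALT/AST, eosinophil percentage | ALT/AST yes; CBC no |

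**Where else could an INR come from?** There are two routes to an ALT or AST above 3xULN.

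1. *Found on a scheduled draw.* An INR might accompany it if the Visit Table lists one, or if the site's LFT panel includes one. Neither can be checked from the text reviewed.
2. *Found on an unscheduled draw* (dose increase after escalation, change in another drug, or symptoms). Section 4b itemises that draw without INR, and the repeat within 72 hours is itemised without INR as well. On this route neither draw requires the test, whatever the Visit Table says. An INR from a scheduled visit at another date would not show coagulation at the time of the elevation.

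**When would the gap matter?** Only when all of the following hold together:

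- ALT or AST is above 3xULN, is not above 8xULN, and has not been above 5xULN for more than 2 weeks;
- TBL is not above 2xULN;
- none of the listed symptoms or signs, and no eosinophilia above 5%, is present;
- INR is above 1.5.

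For illustration, a subject with ALT at 4xULN, TBL not above 2xULN, none of the listed findings and an INR above 1.5 meets item 8 through INR alone.

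**Eosinophilia.** Section 4a draws the CBC on the same schedule as the LFTs, so an elevation found on a scheduled draw comes with a CBC. An elevation found on an unscheduled draw does not, and the repeat does not name one. The gap is similar but smaller and is secondary here.

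**The case against.** The strongest reply is that the panel is expressly a floor. An investigator applying item 8 knows that INR decides continuation once ALT or AST exceeds 3xULN, and is free to order it. Item 8 also accepts any laboratory result and does not say that the rule is read only on the 72-hour draw. Section 4b refers to the Visit Table for visit details, and that table may schedule an INR.

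Much of this stands. A reader might infer that the INR limb rests wholly on the investigator's discretion, or that INR is measured nowhere in the trial. The documents do not support either inference: the Visit Table is not in the text reviewed, LFT is undefined, and the absence of INR from the remaining text cannot show that the plan lacks it.

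The reply does not remove the mismatch on the 72-hour draw. Its content is itemised in Section 4b and depends on neither the Visit Table nor the meaning of LFT. Permission to add a test is not a requirement to add it, and a scheduled INR would not cover an elevation first found on an unscheduled draw.

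It is also fair to say that the exposure is small. Exclusion criterion 4 keeps out liver disease such as cirrhosis, decompensated disease and chronic hepatitis, as well as active bleeding diathesis, so those existing causes of a raised INR are screened out. The remaining item 8 criteria, close follow-up, clinical removal and the toxicity stop all continue to apply. These safeguards limit the consequence; they do not supply the missing test.

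**Conclusion.** The point holds, as a minor one. The tests required on the 72-hour repeat draw allow the bilirubin limb of the >3xULN criterion to be evaluated, but not the INR limb. An INR is permitted on that draw and not required.

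The conclusion rests on the itemised panel in Section 4b and makes no claim about scheduled laboratory tests. A reader might go further and infer that subjects will stay on CBD when the rule says stop. The documents do not show that: other stops may act first, the investigator may order the test, and nothing in the plan indicates how often the combination would arise. Among 10 planned subjects the number affected cannot be estimated and may be zero.

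Seizure frequency and the other outcome variables in Section 7 do not use INR, so no endpoint or analysis changes.

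**What to change.** In Section 4b, Study Visits, add PT/INR to the tests required on the repeat draw within 72 hours of ALT or AST above 3xULN. Leave the item 8 thresholds as they are. Check the Visit Table when drafting. Even if it schedules an INR, the addition is still useful for elevations found on unscheduled draws.

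PT/INR need not be added to the draws prompted by a dose increase, a drug change or symptoms. INR cannot trigger item 8 unless ALT or AST is above 3xULN, and that result already leads to the 72-hour draw.

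As a secondary suggestion, include a CBC with differential on the repeat when the elevation came from an unscheduled draw without one, so that the eosinophilia criterion can be read.

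The cost is a wording amendment and a slightly larger sample on a draw that is already mandatory, with no new visit. The sample volume matters most in infants, since subjects are eligible from 1 month of age. The documents do not say how often this draw will occur.

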### *c. Blinding, including justification for blinding or not blinding the trial, if applicable.*

During this pilot expanded access study, where the primary objectives are to assess tolerability and dose, blinding is not appropriate. There is no placebo or non-treatment group that would require blinding.

### *d. Justification of why participants will not receive routine care or will have current therapy stopped.*

Participants will receive routine care and will not have to stop any of their current anticonvulsants. They will be clinically managed by [name] who will respond to side effects or worsening of the participants' care in a manner consistent with the participants' best interest, including the removal of the participant from the trial.

### *e. Justification for inclusion of a placebo or non-treatment group.*

Not applicable for this first small expanded access study.

*f. Definition of treatment failure or participant removal criteria.*

Treatment failure will be defined as less than a 50% reduction in seizure frequency compared to baseline seizure frequency. Treatment failure will be initially assessed 14 weeks after starting drug (or 8 weeks after reaching steady state) and will be reassessed at every visit thereafter. A subject may continue with only a 30% reduction in seizure frequency if the drug is well tolerated compared to previously tried anticonvulsants. If the subject experiences a temporary increase in seizures at the time treatment failure is assessed, [name] may take the temporary nature of the increase into account. She may also look at the overall reduction in seizure frequency since treatment initiation in determining whether a subject should be withdrawn. If the subject has had other benefits to mood, behavior, or neurologic exam that outweighed the risk from an increase in seizures, then [name] may decide to decrease the dose of the study drug since it has been observed that some subjects do well at doses lower than 25mg/kg/day.

**Participant removal criteria:** If a participant experiences a significant decline in his or her health or wellbeing, the PI will remove the participant from the study. This could include a significant worsening of seizures, or the occurrence of intolerable side effects.

**Treatment will continue until any of the following take place:**

1. Loss of seizure control defined as an increase of 50% in the average weekly number of seizures for a minimum of 4 weeks as compared to the average weekly number of partial-onset seizures during the 8 weeks baseline period. At this point, the subject's CBD dose can be decreased without requiring immediate withdrawal. The subject does not need to be withdrawn unless the seizure frequency does not drop below the 50% increase on the lowered dose.
2. Use of rescue medications longer than the maximum duration determined during the Baseline period.
3. Intolerable toxicity.
4. Treatment failure as defined above.
5. Pregnancy.
6. Withdrawal of consent.
7. Treatment duration completed as per protocol: completion of the Core phase (if patients do not accept to start the extension phase) or completion of the Extension phase.
8. Laboratory results indicate that the subject's liver function test (ALT or AST) has increased in any of the following ways:
  - >8xULN
  - >5xULN for more than 2 weeks
  - >3xULN **and** either (TBL >2xULN **or** INR >1.5)
  - >3xULN with the appearance of fatigue, nausea, vomiting, right upper quadrant pain or tenderness, fever, rash, and/or eosinophilia (>5%)

*g. Description of what happens to participants receiving therapy when study ends or if a participant's participation in the study ends prematurely.*

At study's end GW Pharmaceuticals will continue to provide drug to any patient doing well on Epidiolex and wanting to remain on it (extension study), at least until they have obtained an indication for pediatric epilepsy and it can be billed to the patient's insurance company. All others will be weaned off of the study drug over a month and seen back for one final follow-up visit one month later. For those discontinued specifically due to elevated liver function tests, they will continue to be followed until all abnormalities return to the baseline state as assessed by the investigator with AST or ALT <3xULN. Any patient removed early from the study, and all participants at the end of the study wishing to remain

**PROPRIETARY MATERIALS OF THE HUGO W. MOSER RESEARCH INSTITUTE AT KENNEDY KRIEGER, INC. DO NOT USE OR DISCLOSE WITHOUT PERMISSION OF THE RESEARCH INSTITUTE**

[name] patient will continue to be cared for by [name] and seen at the Hunter Nelson Sturge-Weber Center.

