#### **Measurement of changes in seizures (Routine)**

Change in seizure frequency is the primary outcome measure for this pilot trial. All seizure types will be classified before study entry. Seizure frequency for each seizure type will be recorded during a baseline of 8 weeks before administration of CBD. Seizure type, frequency will be monitored during baseline and treatment as recorded in a patient diary (see seizure log). For assessing the efficacy of CBD, the investigator will count the change in the frequency of seizures (i.e., tonic seizures, clonic seizures, tonic-clonic seizures lasting more than 3 seconds, focal motor seizures, focal seizures with impaired consciousness, atonic seizures, myoclonic seizures including myoclonic absences). In addition, parents/caregivers will report the following **secondary outcome measures**:

- Change in average seizure duration by seizure type
- Change in the number of episodes of status epilepticus, defined as convulsive seizure lasting longer than 10 minutes
- Change in the number of uses of rescue medication
- Change in the number of ER visits/ hospitalizations

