## 5. Inclusion/Exclusion Criteria

**Inclusion criteria:** Participants with Sturge-Weber syndrome brain involvement as defined on neuroimaging (n=10 subjects, male and female, ages 1 month to 45 years of age) and the following:

1. Documentation of a diagnosis of drug resistant epilepsy as evidenced by failure to control seizures despite appropriate trial of two or more AEDs at therapeutic doses. **Drug resistant epilepsy for this study is defined as:** At least 1 reported quantifiable (no cluster or innumerable) defined seizure with motor signs per month for at least 3 months prior to initial visit and during the period between Visit 1 (Screening Visit) and Visit 2 (Baseline Visit), as per data captured in daily seizure diaries. These can be focal seizures, focal seizures with impaired consciousness, myoclonic seizures, generalized, and secondarily generalized seizures.
2. Between 1-5 baseline anti-epileptic drugs at stable doses for a minimum of 4 weeks prior to enrollment. Vagus nerve stimulator (VNS), ketogenic diet and modified Atkins diet do not count toward this limit.
3. VNS must be on stable settings for a minimum of 3 months prior to enrollment.
4. If on ketogenic or Atkins diet, must be on stable ratio for a minimum of 3 months prior to enrollment.
5. Previous subjects who failed at any point to meet continuation criteria and withdrew early may be considered for re-enrollment under a new subject ID as long as the above inclusion criteria are met. The determination of whether to re-enroll will be made by the PI and sponsor on a case-by-case basis. Re-enrollment can occur no earlier than 4 weeks after the final, post-weaning follow-up visit under the old subject ID.

Written informed consent obtained from the patient or the patient's legal representative must be obtained prior to beginning treatment.

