### Exclusion Criteria:

1. Patients with seizures secondary to metabolic, toxic, infectious or psychogenic disorder or drug abuse or current seizures related to an acute medical illness.
2. Presence of only non-motor partial seizures (without limb or facial movements, eye deviation or head turning)
3. Patients who require rescue medication during the Baseline Phase for more than 6 days.
4. Patients with any severe and/or uncontrolled medical conditions at randomization such as:
  - a. Liver disease such as cirrhosis, decompensated liver disease, and chronic hepatitis (i.e. quantifiable HBV-DNA and/or positive HbsAg, quantifiable HCV-RNA)
  - b. Uncontrolled diabetes as defined by fasting serum glucose > 1.5
  - c. Active (acute or chronic) or uncontrolled severe infections
  - d. Active, bleeding diathesis
5. Patients who have had a major surgery or significant traumatic injury within 4 weeks of study entry. Patients who have not recovered from the side effects of any major surgery (defined as requiring general anesthesia), or patients that may require major surgery during the course of the study.

PROPRIETARY MATERIALS OF THE HUGO W. MOSER RESEARCH INSTITUTE AT KENNEDY KRIEGER, INC. DO NOT USE OR DISCLOSE WITHOUT PERMISSION OF THE RESEARCH INSTITUTE

6. Patients who change the dose of the AEDs during 4 weeks before screening or during the baseline period.
7. Prior treatment with any investigational drug or use of any other cannabis product within the preceding 4 weeks prior to study entry.
8. Patients with a history of non-compliance to medical regimens or who are considered potentially unreliable or will not be able to complete the entire study. Those in foster care, unable to keep follow-up appointments, maintain close contact with Principal Investigator, or complete all necessary studies to maintain safety.
9. Pregnant or nursing (lactating) women, where pregnancy is defined as the state of a female after conception and until the termination of gestation, confirmed by a positive hCG laboratory test.

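### Item 1 of the section 4f continuation rules sets on-treatment seizures of no stated type against baseline partial-onset seizures only, so its 50% threshold does not compare like with like

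*Combined protocol and SAP*

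**What the plan says.** In the combined protocol and SAP, section 4f lists the events that end treatment. Item 1, loss of seizure control, is a 50% increase in the weekly average of "seizures for a minimum of 4 weeks as compared to the average weekly number of partial-onset seizures during the 8 weeks baseline period". When it is met, the "CBD dose can be decreased without requiring immediate withdrawal". The next step is: "The subject does not need to be withdrawn unless the seizure frequency does not drop below the 50% increase on the lowered dose".

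Three other places bear on the comparison:

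- **Eligibility (section 5).** Inclusion criterion 1 says of the qualifying seizures: "These can be focal seizures, focal seizures with impaired consciousness, myoclonic seizures, generalized, and secondarily generalized seizures". Exclusion criterion 2 is the only criterion that names partial seizures. It removes subjects with "Presence of only non-motor partial seizures" and does not require a partial-onset seizure.
- **Counting (section 4a, Measurement of changes in seizures).** The efficacy count includes, among others, "focal seizures with impaired consciousness, atonic seizures, myoclonic seizures including myoclonic absences". On baseline data it says: "Seizure frequency for each seizure type will be recorded during a baseline of 8 weeks before administration of CBD".
- **Treatment failure (section 4f).** A subject fails with a reduction of under 50% from baseline seizure frequency, with no type restriction in either period. This is first assessed at week 14, or 8 weeks after steady state. A 30% reduction may suffice if the drug is well tolerated compared with earlier anticonvulsants, and the investigator has further discretion.

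**The concern.** A percentage increase has meaning only if the same thing is counted in both periods. In item 1 the type restriction appears in the baseline period only, and nothing elsewhere limits the on-treatment count or defines seizures as partial-onset. Any seizure that is not partial-onset then adds to the on-treatment count but not to the baseline count, which lowers the real threshold. The alternative reading, partial-onset in both periods, removes that bias but leaves item 1 blind to worsening of the other types. The text does not say which reading applies.

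Item 1 supplies the numeric line for a dose decrease and then for withdrawal, and the lowered-dose step refers back to the same line. Until treatment failure is first assessed, it is the only numeric rule for rising seizure frequency, and that period includes titration. It can also conflict with the treatment-failure rule: the same diary could pass one and meet the other.

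**Working it through.** The plan gives no figure to reproduce; section 7c says that no sample size calculation was done. The check is algebra on the rule.

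**Inputs.** The 50% threshold, the minimum of 4 weeks and the 8-week baseline come from section 4f, item 1. The treatment-failure limits of 50% and, by exception, 30% come from section 4f. Let f be the share of a subject's baseline seizures that are not partial-onset. The documents do not give f, so it is varied from 0 to 1. Let R be the on-treatment weekly total divided by the baseline weekly total. A 50% increase is read as at least 50%, and the 4-week condition as the average over the qualifying weeks. If every week must exceed the line, the same ratio applies week by week.

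**Literal reading.** The baseline comparator is (1-f) times the baseline total, so item 1 is met when R ≥ 1.5(1-f). The true change in total seizures at the line is 1.5(1-f) - 1:

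| f | True change at which item 1 is met |
|---|---|
| 0 | +50% |
| 0.1 | +35% |
| 0.2 | +20% |
| 1/3 | 0% |
| 0.5 | -25% |
| 1 | undefined (baseline comparator is zero) |

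**Unchanged subject.** Put R = 1: f ≥ 1 - 1/1.5 = 1/3. For illustration, take 6 seizures a week in both periods, of which 4 are partial-onset at baseline. The rule reads (6-4)/4 = +50% and is met. Counted like with like, the change is (6-6)/6 = 0%.

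**Subjects who pass the treatment-failure rule.**

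- 50% reduction, R = 0.5: 1-f ≤ 0.5/1.5 = 0.333, so f ≥ 2/3. For illustration, take 6 a week at baseline, 2 of them partial-onset, and 3 a week on treatment. Item 1 reads (3-2)/2 = +50% and is met.
- 30% reduction, R = 0.7, if allowed to continue: 1-f ≤ 0.7/1.5 = 0.467, so f ≥ 0.53.

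**Lowered-dose step.** To fall below the line, R must be under 1.5(1-f). At f = 1/3 the total must be below baseline. At f = 0.5 it must be below 0.75 of baseline, a reduction of more than 25%. Counted like with like, it need only be less than 50% above baseline.

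**Partial-onset in both periods.** Suppose f = 0.5, partial-onset seizures are unchanged and the other types double. The total becomes 0.5 + 2 × 0.5 = 1.5 times baseline, a 50% rise, while item 1 reads 0%.

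**The case against.** The strongest reply is that an increase in a quantity, compared with its baseline, presupposes the same quantity in both periods. A clinician would probably count either partial-onset seizures in both or all seizures in both, and an unchanged subject then reads 0%. That is plausible, and the treatment-failure rule, which is unrestricted in both periods, supports a drafting slip. But the two like-with-like readings give different rules, and the text chooses neither.

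A second reply is that non-partial-onset seizures may be uncommon here. Enrolment requires Sturge-Weber brain involvement on imaging, the background section names focal seizures, secondarily generalized seizures are partial-onset, and the section 4a list does not sort tonic, atonic or myoclonic seizures by onset. This stands as a limit on size. It does not remove the mismatch, because inclusion criterion 1 lists generalized seizures separately from secondarily generalized ones.

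A third reply is that other safeguards cover the gap. Of the decline in health that leads to removal, section 4f says: "This could include a significant worsening of seizures, or the occurrence of intolerable side effects". That carries no type restriction and no number, and section 7c has continuation decided at each visit or contact. This also stands, and it is the main reason the point is minor. Discretion works around item 1 without settling what it counts.

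A reader might infer that unchanged subjects will be wrongly taken off treatment. The documents do not support that. It needs the literal reading and f of at least 1/3. The dose can be lowered first, although a count that stays unchanged would remain over the line. And a subject with no reduction is a treatment failure at the first assessment in any case, subject to discretion. For that subject the slip mainly brings a dose decrease or withdrawal forward.

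**Conclusion.** The comparator in item 1 is wrong as written, and no other section resolves it. On the literal reading, the threshold falls from the intended +50% to 0% at f = 1/3 and -25% at f = 0.5. The more consequential case is a subject who passes the treatment-failure rule yet meets item 1. That needs f of at least 2/3 at a 50% reduction, or 0.53 at a 30% reduction where continuation is allowed, so more than half of the baseline seizures would have to be of other types.

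The point is minor. A subject with only partial-onset seizures is unaffected, and how many of the 10 subjects are affected cannot be known from the documents; it may be none. Two larger conclusions may tempt a reader, and neither is supported. The primary outcome is not compromised, because seizure frequency is defined separately from item 1. Nor do the documents show that the slip would set off the section 7c enrolment stop. That stop counts three removals for side effects or lack of benefit, and the plan does not say that a withdrawal under item 1 is classed as either.

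The arithmetic rests on the assumed range for f and on reading the threshold as at least 50% of an average weekly rate.

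**What to change.** In section 4f, item 1, delete *partial-onset* and state that the on-treatment and the 8-week baseline weekly counts use the same seizure types, namely all quantifiable seizures recorded in the diary. Keep the 50% threshold, the 4-week duration and the dose-lowering step. An unchanged subject then reads 0% whatever the seizure mix, and item 1 matches the treatment-failure rule.

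Do not import the section 4a list for this purpose. It is given for assessing efficacy and omits some types, such as focal seizures that are neither motor nor with impaired consciousness. Using it would narrow a safety rule without saying so.

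The cost is one phrase. No new data are needed, because section 4a already has frequency recorded by type at baseline, and type and frequency recorded in the diary on treatment.
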